12.7 Study Contact Information

Questions regarding safety or medical procedures should be directed to Medtronic. All other questions including emergency contact for reporting serious adverse events and serious adverse device effects should be directed to Medtronic Surgical Innovations (Formerly MITG Surgical Innovations), Clinical Research. Sponsor contact information is subject to change and will be maintained in a document separate from the clinical investigation plan. Sponsor contact information available to sites upon request.

12.8 Product Complaint Reporting

Product complaint reporting and vigilance reporting are applicable, and AEs related to any market-released device during the study must be reported. The reporting of product complaints is not part of the study and should be done in addition to the AE reporting requirements. Refer to local regulations for reporting requirements.

Product Complaint: Any written, electronic, or oral communication that alleges deficiencies related to the identity, quality, durability, reliability, safety, effectiveness, or performance of a medical device that has been placed on the market.

It is the responsibility of the investigator to report all product complaint(s) associated with a medical device distributed by Medtronic, regardless whether they are related to intended use, misuse, or abuse of the product. Reporting must be done immediately and via the regular channels for market-released products. The reporting of product complaints by the clinical team must be done according to the local Standard Operating Procedures. Medtronic will notify the RAs (e.g., CA) as applicable for the following incidents immediately upon learning of them and is not limited to AEs and DDs only:

- Any malfunction or deterioration in the characteristics and/or performance of a device, as well as any inadequacy in the labeling or instructions for use which led or might have led to the death or serious deterioration in the state of health of a patient, user, or other person.
- Any technical or medical reason resulting in withdrawal of a device from the market by the manufacturer.
- Any serious deterioration in the state of health, including:
 - Life-threatening illness or injury
 - Permanent impairment of a body function or permanent damage to a body structure

MDT17051PDS Version 4.0 Page 40 of 56

 A condition necessitating medical or surgical intervention to prevent permanent impairment of a body function or permanent damage to a body structure

13. Data Review Committees

13.1 Independent Medical Monitor

Medtronic will utilize an Independent Medical Monitor to provide an independent adjudication of prespecified adverse events in support of protocol defined endpoint data. The Independent Medical Monitor will be a surgeon in the field of hernia surgery, who is board certified/board eligible, qualified by education and training, and relevant experience appropriate to the use of the product and associated procedures that is not affiliated with an investigative center. The Independent Medical Monitor will contribute to safety aspects of the clinical study and will review any potential adverse events collected related to the procedure/product, and all SAEs as determined by sponsors or sites.

The Independent Medical Monitor will be blinded to the investigational sites.

14. Statistical Design and Methods

14.1 Statistical Test Methods & Analysis Populations

Statistical analysis consists mainly of a descriptive analysis, and will be performed on:

- the Full Analysis Set (FAS, including any subject enrolled and receiving study device) representing the primary analysis population,
- the Per Protocol Analysis Set [PPAS, a subset of the FAS of subjects who meet the primary endpoint (12-month assessment) and who did not deviate (major) from the protocol], as confirmatory analysis and,
- the Safety Analysis Set (any subject with skin incision including those who are 'screen failure during surgery') for safety and efficacy analysis

Continuous variables will be summarized using counts, means, standard deviations, medians, minimum and maximum. Categorical variables will be summarized using frequencies and percentages.

Time to events analyses using Kaplan Meier estimates and curve will be performed for time to recurrence or to adverse event occurrence

Changes to the planned statistical analysis as defined in the protocol will be documented in the statistical analysis plan and clinical study report.

Statistical analysis will be performed using SAS version 9.4 and Minitab® Version 15.0.

MDT17051PDS Version 4.0 Page 41 of 56

For the purposes of study analysis and statistics adverse event will be defined as procedure related adverse events and adverse device effects.

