12.6 Adverse Event and Device Deficiency Reporting Requirements

Investigators are obligated to report applicable adverse events to the study sponsor and in accordance with reporting requirements of their IRB.

Events will be reviewed by the sponsor to determine any reporting obligations to IRBs and regulatory authorities.

SAEs need to be reported to the sponsor within 24 hours of becoming aware.

Assessment of the occurrence of an AE will be based on changes in the subject's physical examination, laboratory results and/or signs and symptoms. Adverse events will be monitored until a subject completes the study, or unless the Investigator determines the event is related to the device, in which case they will be monitored until resolution if possible. Medical care will be provided, as defined in the informed consent, for any AE related to study participation. Adverse events will be collected on an AE eCRF and applicable source documentation. To the extent possible, the event to be recorded and reported is the event diagnosis as opposed to event symptoms (e.g., fever, chills, nausea and vomiting in the presence of a clinically diagnosed infection is to be reported as infection only). For subjects who are screen failure during surgery (Section 10.12.2.2) AEs will be recorded at time of enrollment until discharge. For other subjects, AEs occurring at time of enrollment and up to and including 24 months follow-up will be recorded.

The following should not be considered an AE:

- A condition requiring a preplanned procedure unless the condition worsened since screening
- A pre-existing condition found at the time of screening, unless the condition has worsened since enrollment.

All responses to the above events that require treatment beyond the institution's standard procedures must be reported.

MDT17051PDS Version 4.0 Page 39 of 56

All AEs observed during the course of this study, regardless of severity, seriousness, or relationship to the device and procedure will be recorded on the appropriate AE eCRF.

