[Final v3.0]	 Page 1: Update of CIP version: V4.0 (2021 12 03) Section 5 page 8: Add of "Remote or phone follow-up, medical record review, or follow-up with other healthcare practitioner may be utilized for 1-month, 3-month, 12-month and 24-month visits due to COVID-19 related reasons as explained in the CIP v4.0 and the Addendum VA." Section 7.9 pages 14/15: Removal of "and procedure related adverse events" Add of "Time to Device-related AEs occurrence may also be assessed using Kaplan Meyer estimates." Add of "Hernia recurrence will be assessed during physical examination at 1-month, 3-month, 12-month and 24-month assessment post-surgery. Remote follow-up visits due to COVID-19 related reasons may be performed: if hernia or hernia reoccurrence is suspected during a remote visit using questionnaires, the subject will be instructed to return to the clinic or hospital for diagnosis by the surgeon through clinical assessment. This process is fully accepted by scientific societies^{5,6,7,8,6}". Section 9 pages 17/18: Move of all the references in this section (instead of footnotes) and add of new references related to remote visits. 	[name], Sr Biostatistician, Global Clinical Data Solutions

Version [Final v3.0]

2. List of Abbreviations and Definitions of Terms

Term/Abbreviation	previation Definition					
ADE	Adverse device effect - Adverse event related to the use of an investigational medical device. NOTE 1: This definition includes adverse events resulting from insufficient or inadequate instructions for use, deployment, implantation, installation, or operation, or any malfunction of the investigational medical device. NOTE 2: This definition includes any event resulting from use error or from intentional misuse of the investigational medical device					
AE	Adverse event - Any untoward medical occurrence, unintended disease or injury, or untoward clinical signs (including abnormal laboratory findings) in subjects, users or other persons, whether or not related to the investigational medical device. NOTE 1: This definition includes events related to the investigational medical device or the comparator. NOTE 2: This definition includes events related to the procedures involved. NOTE 3: For users or other persons, this definition is restricted to events related to investigational medical devices.					
ASA	American Society of Anesthesiologists					

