7.8.1. First interim Analysis

Preliminary analysis will be conducted in the study when 30 enrolled subjects complete the 3 month follow-up time-point. The objective is to confirm safety of the product at 3 months. This 3-month time-point is consistent with the wound healing period and the Parietene™ DS Composite Mesh film degradation profile (completely degraded by bulk hydrolysis in less than 15 weeks). This interim analysis is driven by regulatory needs, to support CE marking submission.

Version [Final v3.0]

Through analysis of clinical data available on a predicate device (Proceed[™] surgical mesh) and similar Medtronic composite meshes (Parietene[™] Composite mesh, Parietex[™] Composite mesh) used in ventral hernia repair (primary and incisional) by open or laparoscopic approach assessed during short-term post-surgery report the following adverse event rates:

10.6% on the equivalent, Proceed[™] surgical mesh used in laparoscopic ventral hernia repair at 3-6 weeks followup²,

14.3% on Parietene[™] Composite mesh used in laparoscopic ventral hernia repair at 10 weeks follow-up (range 6-25 weeks)³,

To 25%, on Parietex[™] Composite mesh used in laparoscopic and open ventral hernia repair after 2 months followup with a population of 30 subjects⁴.

Based on these studies, adverse event rates were estimated to range between 11% and 25% and used to generate binomial probabilities to observe at least 1 or 2 AEs with a sample size of 30 subjects as shown in the table below.

N=30 subjects	Hypothetic procedure related adverse event rate					
prob. to observe:	11%	12%	14%	17%	20%	25%
≥ 1 AE	97.0%	97.8%	98.9%	99.6%	99.9%	100.0%
≥ 2 AEs	85.7%	89.0%	93.6%	97.3%	98.9%	99.8%

With an N=30 of enrolled and evaluable subjects at the time of interim analysis, and assuming an 11% adverse event rate, there is a 97% probability to observe at least 1 adverse event and an 85.7% probability to observe at least 2 adverse events. In addition, the probability to observe adverse events increases as the adverse event rate increases to a maximum of 100% and 99.8% for observation 1 and 2 adverse events respectively at an adverse event rate of 25%.

First interim analysis (Safety analysis at 3-months) will evaluate subject's disposition, screening data, demographics and occurrence of procedure or device-related AE occurring within 3-month from surgery, including:

PPDS Statistical Analysis Plan		
Version [Final v3.0] Page 14 of 1	3	Medtronic

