➔ Incidence of procedure and/or device-related AE occurring within 3 month from-surgery overall, and according to:

- \circ Relation to the procedure
- \odot Relation to the device including anticipated and unanticipated ADEs,
- \circ Severity,
- \circ Seriousness

 $_{\odot}$ Time of AE occurrence (intra-operatively, between surgery and discharge, and within 1 and 3 months post-surgery)

- → Incidence of procedure and/or device-related AE occurring within 3 month from-surgery by SOC and PT
- → Incidence of procedure and/or device-related SAE occurring within 3 month from-surgery by SOC and PT
- → Listing of procedure and/or device-related AE
- → Listing or procedure and/or device-related SAE

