Hernia recurrence will be assessed during physical examination at 1-month, 3-month, 12-month and 24-month assessment post-surgery. Remote follow-up visits due to COVID-19 related reasons may be performed: if hernia or hernia reoccurrence is suspected during a remote visit using questionnaires, the subject will be instructed to return to the clinic or hospital for diagnosis by the surgeon through clinical assessment. This process is fully accepted by scientific societies^{5,6,7,8,9}

7.10.Safety Evaluation

Safety will be assessed as the proportion of subjects with AE based on the FAS, PPAS and SAS; AE incidence will be reported overall, and according to:

- Relation to the procedure
- Relation to the device including anticipated and unanticipated ADEs,
- Severity,
- Seriousness.

PPDS Statistical Analysis Plan	
Version [Final v3.0] Page 16 of 18	Mectronic

Listing of AEs, SAEs, ADEs and SADEs, and UADEs will be provided based on FAS, PPAS and SAS, using the MEDRA coding system classification for AE terms, and including characteristics described previously and AE outcome.

7.11.Health Outcomes Analyses

Health outcomes analyses are already part of primary and secondary endpoints analyses, as described previously.

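### Protocol 14.1 narrows the analysis meaning of adverse event to related events while SAP 7.10 and Protocol 14.4 do not, and the first interim has no all-cause SAE or death output

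*Protocol*

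**What the plan says.** Protocol 12.6 sets a full collection scope: "All AEs observed during the course of this study, regardless of severity, seriousness, or relationship to the device and procedure will be recorded". Protocol 14.1 then narrows the term for study analysis and statistics: "adverse event will be defined as procedure related adverse events and adverse device effects". Protocol 14.4 plans the incidence of SAEs on all three analysis sets and attaches no relatedness condition to them.

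The SAP glossary keeps the wide meaning, with an AE counted "whether or not related to the investigational medical device". SAP 7.10 uses the term without qualification: "Safety will be assessed as the proportion of subjects with AE based on the FAS, PPAS and SAS". SAP 7.12, which records departures from the protocol's statistical methods, covers analysis sets only.

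For the first interim, SAP 7.8.1 gives the trigger ("Preliminary analysis will be conducted in the study when 30 enrolled subjects complete the 3 month follow-up time-point") and the purpose ("This interim analysis is driven by regulatory needs, to support CE marking submission"). Its event scope is the "occurrence of procedure or device-related AE occurring within 3-month from surgery". The outputs follow that scope, for example "Incidence of procedure and/or device-related SAE occurring within 3 month from-surgery by SOC and PT", and both listings carry the same restriction.

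**The concern.** Two things are at stake.

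The first is that one quantity, the overall proportion of subjects with an AE, has two definitions in force. A programmer following Protocol 14.1 drops subjects whose only events are unrelated; one following the SAP glossary and 7.10 keeps them. Protocol 14.1 itself requires changes to the planned analysis to be documented in the SAP, and this one is not.

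The second is that the first interim is meant to confirm 3-month safety for a regulatory submission, yet its safety outputs contain only events that have passed a causality filter. The study is single-arm and unblinded, so there is no control group against which to judge that filter. All-cause SAEs and deaths are the usual complement because they do not depend on attribution. The filter also has a feature that matters here: under Protocol 12.5.1, a complication of a procedure counts as not related if the subject would have had that procedure without the device. Every subject is having elective ventral hernia repair, so serious complications of the repair can be classed as unrelated and leave the interim tables.

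**Working it through.** **Step 1: the texts side by side.**

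| Place | Events in scope |
|---|---|
| Protocol 12.3 Table 1 and 12.6 | All AEs, any relationship |
| Protocol 14.1 (analysis definition) | Procedure-related AEs and ADEs |
| Protocol 14.4 | ADEs, SAEs, SADEs; no relatedness limit on SAEs |
| SAP section 2 | All AEs, any relationship |
| SAP 7.8.1 (first interim) | Related AEs and SAEs only, in every table and listing |
| SAP 7.10 | AE, unqualified; AEs and SAEs also listed |
| SAP 7.12 (log of changes) | Analysis sets only |

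At the first interim, Protocol 14.1 and SAP 7.8.1 agree, and the scope is narrow. For the later safety evaluation they diverge: SAP 7.10 with the glossary is wide, Protocol 14.1 is narrow, and Protocol 14.4 is wide unless 14.1 is read as governing it.

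**Step 2: the plan's own interim figures.** Protocol 14.2 and SAP 7.8.1 give the probability of seeing at least 1 or at least 2 AEs among 30 subjects. With event rate p:

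- P(at least 1) = 1 − (1 − p)^30
- P(at least 2) = 1 − (1 − p)^30 − 30p(1 − p)^29

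At p = 0.11 these give 96.97% and 85.73%, against 97.0% and 85.7% stated. At p = 0.25 they give 99.98% and 99.80%, against 100.0% and 99.8%. All 12 cells agree to within 0.1 point. The table is headed as a procedure-related rate, so it matches the narrow scope. There is no arithmetic error.

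**Step 3: size of the interim gap.** The documents give no rate for SAEs classed as unrelated, so the risk u below is an assumption shown as a range. The chance that at least one of 30 subjects has such an SAE by 3 months is 1 − (1 − u)^30, and the expected number of affected subjects is 30u.

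| Assumed u | Chance of at least one in 30 | Expected subjects |
|---|---|---|
| 1% | 26% | 0.3 |
| 2% | 46% | 0.6 |
| 3% | 60% | 0.9 |
| 5% | 79% | 1.5 |
| 10% | 96% | 3.0 |

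Each subject whose only SAE is classed as unrelated moves the SAE proportion by 1/30 = 3.3 points.

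**Step 4: the two values of the overall AE rate.** Take the plan's lower related rate, r = 11%, and assume an independent risk u of an unrelated AE. The all-AE rate is 1 − (1 − r)(1 − u):

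- u = 1%: 1 − 0.89 × 0.99 = 11.9%
- u = 10%: 1 − 0.89 × 0.90 = 19.9%

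The narrow definition reports 11% in both cases. This illustrates the mechanism and is not a forecast: the 11% is a short-term rate taken from the plan, and u is assumed.

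**The case against.** The strongest reply is that the interim scope is a deliberate, prespecified choice on which protocol and SAP agree, and that safeguards surround the causality call. Under Protocol 13.1 an independent medical monitor, unaffiliated with any site, reviews all SAEs. Protocol 14.2 reconciles assessments and takes the most conservative one. Protocol 12.5.1 classes events that cannot be assessed as possibly related. All of this stands and reduces miscoding. It does not place an SAE finally classed as unrelated into any interim AE/SAE output, and Protocol 14.2 makes the monitor or sponsor assessment conditional on being applicable.

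A reader might infer more than the documents support:

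- *Unrelated SAEs are lost from the whole study's reporting.* Not shown. Protocol 14.4 and SAP 7.10 name SAEs without a relatedness limit, so for later analyses the problem is ambiguity, not certain omission.
- *An unrelated death would appear nowhere at the interim.* Not shown. The interim covers subject disposition, SAP 7.1.1 tabulates discontinuation reasons, and Protocol 10.12.3 lists death as an exit reason. Also, a subject who dies before 3 months is not one of the 30 completers. The documents do not say whether the interim tables are limited to completers, so an absence could come from that trigger, and the 1/30 arithmetic would not describe it.
- *The layout of SAP 7.10, overall and then by relation, proves that it counts all AEs.* It does not, because SAP 7.8.1 uses the same layout for related-only events. The wide reading rests on the glossary and the unqualified term.
- *The interim safety result rests wholly on an unblinded judgement by investigator and sponsor.* The monitor and the conservative rule make that too strong.

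Finally, the 3.3-point step holds for any binary outcome with 30 subjects and does not measure this defect.

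**Conclusion.** The concern holds in two parts. First, the meaning of AE differs between Protocol 14.1 on one side and the SAP glossary, SAP 7.10 and Protocol 14.4 on the other, and SAP 7.12 does not record it. The overall AE rate at the final analysis, and at 12 months so far as safety is reported then, depends on which text is followed. Second, at the first interim an SAE classed as unrelated appears in no AE/SAE table or listing, and a death so classed could appear only as a disposition reason without event detail.

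The loss is in reporting, not in collection. Its size cannot be derived from the documents; the 26% to 96% range rests on assumed unrelated-SAE risks of 1% to 10% and on independence between subjects.

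**What to change.** - **Protocol 14.1:** let AE keep its Table 1 meaning, and use a separate term, related AE, for procedure-related AEs and ADEs.
- **Protocol 14.4 and SAP 7.10:** state that both use the full definition, and log the clarification in SAP 7.12.
- **SAP 7.8.1:** beside the existing related-event outputs, add incidence by SOC and PT and a listing of all SAEs and all deaths regardless of relationship. If that interim has already been run, issue these as a supplement.

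The cost is a few wording edits and a few extra outputs from data that Protocol 12.6 already collects. The reported SAE rate may be higher than under the related-only scope; showing both sets together lets the reader see why.

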14.2 Interim Analysis

Preliminary analysis will be conducted in the study when 30 enrolled subjects complete the 3-month follow-up time-point. The objective is to confirm safety of the product at 3 months. This 3-month time-point is consistent with the wound healing period and the Parietene™ DS Composite Mesh film degradation profile (completely degraded by bulk hydrolysis in less than 15 weeks). This interim analysis is driven by regulatory needs, to support CE marking submission.

Through analysis of clinical data available on a predicate device (Proceed™ surgical mesh) and similar Medtronic composite meshes (Parietene™ Composite Mesh, Parietex™ Composite Mesh) used in ventral hernia repair (primary and incisional) by open or laparoscopic approach assessed during short-term post-surgery report the following adverse event rates:

- 10.6% on the equivalent, Proceed™ surgical mesh used in laparoscopic ventral hernia repair at 3-6 weeks follow-up (9),
- 14.3% on Parietene™ Composite mesh used in laparoscopic ventral hernia repair at 10 weeks follow-up (range 6-25 weeks) (10),
- To 25%, on Parietex™ Composite mesh used in laparoscopic and open ventral hernia repair after
 2 months follow-up with a population of 30 subjects (11), we obtain the following binomial probabilities to observe one or more event(s):

[figure not shown]
Based on these studies, adverse event rates were estimated to range between 11% and 25% and used to generate binomial probabilities to observe at least 1 or 2 AEs with a sample size of 30 subjects as shown in the table below.

N=30 subjects	Hypothetic procedure related adverse event rate						
prob. to observe:	11%	12%	14%	17%	20%	25%	
≥ 1 AE	97.0%	97.8%	98.9%	99.6%	99.9%	100.0%	
≥ 2 AEs	85.7%	89.0%	93.6%	97.3%	98.9%	99.8%	

With an N=30 of enrolled and evaluable subjects at the time of interim analysis, and assuming an 11% adverse event rate, there is a 97% probability to observe at least 1 adverse event and an 85.7% probability to observe at least 2 adverse events. In addition, the probability to observe adverse events increases as the adverse event rate increases to a maximum of 100% and 99.8% for observation 1 and 2 adverse events respectively at an adverse event rate of 25%.

An additional interim analysis is planned to occur for completed 12-month follow-up visit data.

MDT17051PDS Version 4.0 Page 42 of 56

For the purpose of the interim analysis and in accordance with regulatory requirements all safety data will utilize MedDRA and are to be assessed using the potential risks identified and defined in Section 12.3. The seriousness and relation of the adverse event to the device and procedure is assessed first by the Principal Investigator of the site, and if applicable by the external Medical Monitor or Internal Medtronic Safety Representative. Reconciliation is made between these assessments and the most conservative assessment will be used.

